Table JGDR.8.	General Guidelines for Olaratumab Dose Modification due to Hematologic Toxicities	47
Table JGDR.9.	Olaratumab Day 8 Dosing Algorithm Based on ANC and Platelet Count	48
Table JGDR.10.	General Guidelines for Olaratumab Dose Modification due to Nonhematologic Toxicities	49
Table JGDR.11.	General Guidelines for Doxorubicin Dose Modification Due to Neutropenia	51
Table JGDR.12.	General Guidelines for Dose Modification of Ifosfamide due to Toxicity	52
Table JGDR.13.	Dose Modification of Ifosfamide due to Hepatic Impairment	53
Table JGDR.14.	Dose Modification of Ifosfamide due to Renal Impairment	54
Table JGDR.15.	Olaratumab Infusion-Related Reaction Treatment Guidelines	57

List of Figures

Figure		Page
Figure JGDR.1.	Illustration of study design.....	29
Figure JGDR.2.	Continued access diagram.....	60

List of Appendices

Appendix		Page
Appendix 1.	Abbreviations and Definitions	79
Appendix 2.	Study Governance, Regulatory and Ethical Considerations	83
Appendix 3.	Clinical Laboratory Tests.....	86
Appendix 4.	Pharmacokinetic, Biomarker, Pharmacogenetics and Immunogenicity Sampling Schedules	87
Appendix 5.	Hepatic Monitoring Tests for Treatment-Emergent Abnormality	91
Appendix 6.	Creatinine Clearance Formula.....	92
Appendix 7.	Fridericia's QT Correction Formula.....	93
Appendix 8.	Protocol Amendment I5B-MC-JGDR(a) Summary A Phase 1b Study of Olaratumab, Doxorubicin and Ifosfamide in the Treatment of Patients with Advanced or Metastatic Soft Tissue Sarcoma	94

1. Synopsis

Protocol Title:

A Phase 1b Study of Olaratumab, Doxorubicin and Ifosfamide in the Treatment of Patients with Advanced or Metastatic Soft Tissue Sarcoma

Rationale:

Study I5B-MC-JGDG (Study JGDG) was a Phase 1b/randomized Phase 2 study evaluating the efficacy of doxorubicin with or without olaratumab in the treatment of advanced soft tissue sarcoma (STS). The study met its primary endpoint for progression-free survival (PFS) (hazard ratio [HR] = 0.67; $p = 0.06$ as compared to a prespecified alpha level of 0.2) with an improvement in median PFS and overall survival (OS) of 2.5 months and 11.8 months, respectively, for olaratumab plus doxorubicin over doxorubicin alone, with a manageable safety profile. The OS HR of 0.46 was highly statistically significant ($p = 0.0003$; Tap et al. 2016). Based on these results, olaratumab has received conditional approval in the United States and European Union in combination with doxorubicin for the treatment of adult patients with STS.

While doxorubicin alone or in combination with other chemotherapeutic agents has been the mainstay of treatment for decades (Linch et al. 2014), in more recent years the combination of doxorubicin, ifosfamide and mesna has demonstrated increased tumor response and PFS compared to doxorubicin alone. However, this regimen is associated with a higher rate of Grade 3 and 4 toxicities and no improvement in OS (Judson et al. 2014), limiting the use of this regimen to distinct clinical settings, such as when shrinkage of the tumor is important and the risk of greater toxicity is felt to represent an acceptable benefit-risk. This regimen has also been evaluated in the neoadjuvant and adjuvant settings for patients with STS (Gortzak et al. 2001; Grobmyer et al. 2004; Pisters et al. 2016).

The positive efficacy results seen with olaratumab in combination with doxorubicin in Study JGDG provide strong rationale for determining whether olaratumab can also be safely added to the doxorubicin, ifosfamide and mesna regimen. It is plausible that the addition of olaratumab to doxorubicin, ifosfamide and mesna may further increase efficacy endpoints such as tumor response rate, PFS and OS, without a clinically significant increase in toxicity. Study I5B-MC-JGDR (Study JGDR) will characterize the safety and tolerability of olaratumab in combination with doxorubicin, ifosfamide and mesna in patients with advanced STS, and if acceptable, determine the dosing regimen of olaratumab in combination with doxorubicin and ifosfamide appropriate for future studies of this combination.

Objectives and Endpoints:

Objectives	Endpoints
Primary	
 To characterize the safety profile of olaratumab when given in combination with doxorubicin, ifosfamide and mesna and to determine the dosing regimen appropriate for a future Phase 2 study
Secondary	
 PK: C_{max} and AUC from time 0 to the last time point with a measurable concentration, and AUC from time 0 to infinity of olaratumab. Other noncompartmental parameters, such as half-life, clearance and volume of distribution may be reported. Plasma doxorubicin and ifosfamide concentrations will be summarized by descriptive statistics Immunogenicity: Anti-olaratumab antibody levels at baseline, during the study, at the 30-day follow-up visit and in the event of olaratumab IRRs Antitumor activity: Radiographic assessments according to RECIST Version 1.1 criteria every 6 weeks (-7 days) until radiographic documentation of PD. Efficacy endpoints will include objective response rate, PFS, duration of response, disease control rate and OS
Exploratory	
 To explore biomarkers related to, but not limited to tumor microenvironment, immune cells/immune functioning, mechanism of action of study drugs, PDGF, cancer-related pathways and disease state, and their association with demographics, disease state and clinical outcomes

Abbreviations: AUC = area under the concentration curve; C_{max} = maximum observed concentration; DLT = dose-limiting toxicity; IRR = infusion-related reaction; NCI-CTCAE = National Cancer Institute-Common Terminology Criteria for Adverse Events; OS = overall survival; PD = progressive disease; PDGF = platelet-derived growth factor; PFS = progression-free survival; PK = pharmacokinetics; RECIST = Response Evaluation Criteria in Solid Tumors; SAE = serious adverse event; STS = soft tissue sarcoma; TEAE = treatment-emergent adverse event.

Overall Design:

Study JGDR is a Phase 1b, multicenter, nonrandomized, open-label study of olaratumab combined with doxorubicin, ifosfamide and mesna in the treatment of patients with advanced or metastatic STS.

Dose-Finding Phase:

Olaratumab 15 mg/kg and Loading Dose Cycle Cohorts – Approximately 15 patients will be initially enrolled and treated with a 15-mg/kg dose of olaratumab (on Days 1 and 8 of a 21-day cycle) in combination with doxorubicin, ifosfamide and mesna and assessed for safety after 1 cycle of therapy. If safety of the 15-mg/kg dose of olaratumab is established, 15 additional patients will be enrolled and receive a 20-mg/kg loading dose cycle of olaratumab on Days 1 and 8 of a 21-day cycle in Cycle 1 only, followed by 15 mg/kg on Days 1 and 8 of subsequent cycles in combination with doxorubicin, ifosfamide and mesna.

Should unacceptable toxicity be observed at the olaratumab 15-mg/kg dose, the study will include an option to explore the same regimen using a reduced ifosfamide dose. Provided safety is established at this lower dose of ifosfamide, a loading dose cycle of olaratumab as previously described will also be explored using the reduced ifosfamide dose.

Dose Confirmation Phase:

If a safe and tolerable dosing regimen of olaratumab is identified, approximately 15 additional patients will be enrolled in a Dose Confirmation Phase to confirm the safety of this treatment regimen for use in any future studies of this combination.

Patients in both study phases will continue treatment for a maximum of 6 cycles, or until there is documented disease progression, unacceptable toxicity, death, or other discontinuation criteria are met. Patients who discontinue doxorubicin, ifosfamide and mesna treatment without evidence of disease progression will receive olaratumab as monotherapy until there is evidence of disease progression, death, intolerable toxicity, or other withdrawal criteria are met. Patients who undergo surgical tumor resection following study treatment are not eligible to receive olaratumab as monotherapy.

Number of Patients: approximately 45-60 total enrolled

Dose-Finding Phase:

Entered: approximately 33-48

Enrolled: approximately 30-45

Dose Confirmation Phase:

Entered: approximately 17

Enrolled: approximately 15

Treatment Arms and Duration:

Phase and Dose Cohort		Drug Name and Dose	Day of 21-day (± 3 days) Cycle	Total Dose
Dose-Finding Phase	Olara 15 mg/kg	Olara 15 mg/kg ^a	D1 and D8	
		Dox 25 mg/m ² per day	D1, D2, D3	75 mg/m ²
		Ifos 2.5 g/m ² per day ^b	D1, D2, D3, D4 ^a	10 g/m ² ^a
		Mesna dose $\geq 60\%$ of ifos dose ^b	D1, D2, D3, D4	
	Loading Dose Cycle	Olara 20 mg/kg Cycle 1	D1 and D8	
		Olara 15 mg/kg Cycles 2 to 6 ^a	D1 and D8	
		Dox 25 mg/m ² per day	D1, D2, D3	75 mg/m ²
		Ifos 2.5 g/m ² per day ^b	D1, D2, D3, D4	10 g/m ²
Dose Confirmation Phase	Olara recommended dose	Olara dose determined from Dose-Finding Phase ^a	D1 and D8	
		Dox 25 mg/m ² per day	D1, D2, D3	75 mg/m ²
		Ifos 2.5 g/m ² per day ^b	D1, D2, D3, D4	10 g/m ²
		Mesna dose $\geq 60\%$ of ifos dose ^b	D1, D2, D3, D4	

Abbreviations: D = day; DLT = dose-limiting toxicity; dox = doxorubicin; g = grams; ifos = ifosfamide; IV = intravenous; kg = kilogram; m² = square meters; mg = milligrams; olara = olaratumab.

a All patients will receive study therapy (olaratumab + doxorubicin/ifosfamide/mesna) for a maximum of 6 cycles, or until a discontinuation criterion is met. Patients who discontinue doxorubicin, ifosfamide and mesna treatment without evidence of disease progression will receive olaratumab as monotherapy until there is evidence of disease progression, death, intolerable toxicity, or other withdrawal criteria are met.

b If DLT rules are exceeded in the olaratumab 15-mg/kg cohort, a reduced dose of ifosfamide (7.5 g/m² total dose) will be explored. This will be accomplished by omitting the Day 4 dose (that is, ifosfamide will be administered at a dose of 2.5 g/m² on D1, D2 and D3). The Day 4 dose of mesna will be correspondingly omitted. A Loading Dose Cycle of olaratumab (20 mg/kg on Days 1 and 8 of C1, then 15 mg/kg on Days 1 and 8 of subsequent cycles) may also be explored in combination with the reduced dose of ifosfamide.

2. Schedule of Activities

Table JGDR.1. Pretreatment Schedule of Activities

Day Relative to C1D1	≤28	≤14	≤7	Instructions
Procedure				
Informed consent	X			ICF must be signed before any protocol-specific procedures are performed. Assessments performed prior to the date of consent may be used as study-required assessments, provided they are appropriately documented.
Inclusion/exclusion criteria			X	
Physical examination			X	Including height, weight and vital signs (temperature, blood pressure, pulse rate, respiration rate)
ECOG performance status			X	
Medical history		X		Including assessment of preexisting conditions and historical illnesses.
Prior and current medication	X			
Prior therapies for treatment of underlying disease		X		
AE collection	X			After consent, collect AEs continuously throughout pretreatment period. CTCAE Version 4.0
Radiologic imaging and measurement of palpable or visible lesions	X			RECIST 1.1 Scans performed prior to the date of consent may be used, provided they are within 28 days of enrollment. Imaging requirements include CT scan or MRI of the chest, abdomen and pelvis and other areas, as clinically indicated. It is recommended that CT imaging of the abdomen/pelvis be performed with IV contrast, whenever possible. If this is not feasible/advisable secondary to hypersensitivity or other conditions, then gadolinium-enhanced MRI is preferred. For patients with known serious allergic reactions to CT contrast material, a CT of the chest without contrast and contrast-enhanced MRI of the abdomen/pelvis are encouraged.
ECG	X			
Echocardiogram and/or MUGA scan	X			
Hematology		X		See Appendix 3 . To be performed locally for patient management and centrally for analysis purposes.
Coagulation		X		See Appendix 3 . To be performed locally.
Clinical chemistry		X		See Appendix 3 . To be performed locally for patient management and centrally for analysis purposes.
Urinalysis		X		See Appendix 3 . To be performed locally.

Serum pregnancy test			X	Applies only to women of childbearing potential. See Appendix 3 . To be performed locally.
Tumor tissue		X		See Section 9.7.2 .
Sample collection				See Appendix 4 .
Pharmacodynamics				
Pharmacokinetics				
Immunogenicity				
Pharmacogenetics				
Other biomarkers				

Abbreviations: AE = adverse event; C1D1 = Cycle 1 Day 1; CT = computed tomography; CTCAE = Common Terminology Criteria for Adverse Events (NCI 2009); ECG = electrocardiogram; ECOG = Eastern Cooperative Oncology Group (Oken et al. 1982); ICF = informed consent form; IV = intravenous; MRI = magnetic resonance imaging; MUGA = multiple-gated acquisition; RECIST 1.1 = Response Criteria in Solid Tumors Version 1.1 (Eisenhauer et al. 2009).

Table JGDR.2. On-Study Treatment Schedule of Activities

Day within Cycle Procedure	Cycles 1-6 (olaratumab + doxorubicin + ifosfamide; (Cycle = 21 days)						Cycles 7-N Olaratumab Monotherapy ^a (Cycle = 21 days)		Instructions
	1	2	3	4	8	15	1	8	
Physical examination	X				X		X		
 • Perform prior to infusion of study drug(s). • Includes weight and BSA.
Vital signs	X	X	X	X	X	X	X		Vital signs include temperature, blood pressure, pulse rate, respiration rate.
Concomitant medication	X						X		Concomitant medications will be recorded continuously throughout the treatment period.
AE collection	X						X		Collect continuously throughout the treatment period; CTCAE Version 4.0.
ECOG performance status	X					X			
Radiologic imaging and measurement of palpable or visible lesions	X						X		
 • Perform according to RECIST 1.1, by the same method used at baseline, q 6 weeks (-7 days) from the start of treatment until radiographic disease progression, death, or study completion, whichever occurs first. • Perform as scheduled, even if study treatment is delayed or omitted.
ECG	X					X			
 • Perform local 12-lead ECG on Day 1 of Cycle 1 through Cycle 6. • Perform local 12-lead ECG on Day 1 of Cycle 7 and approximately 6 months (\pm14 days) and 12 months (\pm14 days) after discontinuation of doxorubicin and ifosfamide treatment
Echocardiogram and/or MUGA scan	X C4 and C6						X		
 • Perform at the end of C4 and C6; perform additional evaluations in the setting of cardiac symptoms and/or at the discretion of the investigator. • For patients receiving olaratumab as monotherapy following discontinuation of combination therapy, perform approximately 6 months (\pm14 days) and 12 months (\pm14 days) after discontinuation of doxorubicin and ifosfamide treatment.
Hematology	X				X	X	X	X	\leq 3 days prior to administration of study treatment on D1 and \leq 1 day prior to administration of study treatment on D8, unless more frequent assessment is clinically indicated. Day 15 labs may be drawn within \pm 1 day of Day 15. See Appendix 3 . To be performed locally for patient management and centrally for analysis purposes.

Day within Cycle Procedure	Cycles 1-6 (olaratumab + doxorubicin + ifosfamide; (Cycle = 21 days)						Cycles 7-N Olaratumab Monotherapy ^a (Cycle = 21 days)		Instructions
	1	2	3	4	8	15	1	8	
Coagulation	X						X		≤3 days prior to administration of study treatment on D1, unless more frequent assessment is clinically indicated. For patients receiving olaratumab as monotherapy following combination therapy discontinuation, perform on D1 of every other cycle. See Appendix 3 . To be performed locally.
Clinical chemistry	X				X	X	X		≤3 days prior to administration of study treatment on D1 and ≤1 day prior to administration of study treatment on D8, unless more frequent assessment is clinically indicated. Day 15 labs may be drawn within ±1 day of Day 15. See Appendix 3 . To be performed locally for patient management and centrally for analysis purposes.
Urinalysis	X	X	X	X					Monitor patients for evidence of micro- and/or macroscopic hematuria and treat according to institutional standards.
Pregnancy test	X						X		
 • Applies only to women of childbearing potential • Where required by local law or regulation, perform once every 21 days (-7 days) prior to administration of study treatment. • To be performed locally
Administer olaratumab	X				X		X	X	Administer IV over 60 (±5) min. Administer until a maximum of 6 cycles is complete, or until PD, unacceptable toxicity, death, or other withdrawal criteria are met. Patients who discontinue doxorubicin, ifosfamide and mesna treatment without evidence of disease progression will receive olaratumab as monotherapy until there is evidence of disease progression, death, intolerable toxicity, or other withdrawal criteria are met. Patients who undergo surgical tumor resection following study treatment are not eligible to receive olaratumab as monotherapy. See section 7.1.1 for olaratumab premedication requirements. See section 7.8.1 for olaratumab IRR monitoring period requirements.
Administer doxorubicin	X	X	X						Administer IV over less than 60 (±5) min or as a continuous IV infusion (according to institutional guidelines) after completion of olaratumab infusion and any required observation period. Administer until a maximum of 6 cycles is complete, or until PD, unacceptable toxicity, death, or other withdrawal criteria are met. See Section 7.1.2 for details of dexamethasone administration.

Day within Cycle Procedure	Cycles 1-6 (olaratumab + doxorubicin + ifosfamide; (Cycle = 21 days)						Cycles 7-N Olaratumab Monotherapy ^a (Cycle = 21 days)		Instructions
	1	2	3	4	8	15	1	8	
Administer ifosfamide	X	X	X	X	*				Administer IV over 3 hours (± 15 min). Administer until a maximum of 6 cycles is complete, or until PD, unacceptable toxicity, death, or other withdrawal criteria are met. *Patients treated in cohorts with ifosfamide dose reduction will have the Day 4 dose omitted (that is, ifosfamide will be administered at a dose of 2.5 g/m^2 on D1, D2 and D3).
Administer mesna	X	X	X	X					See Section 7.1.3 for details of mesna administration.
G-CSF	X								The use of G-CSFs is required. Administer according to ASCO and NCCN guidelines. In general, G-CSF products like filgrastim or pegfilgrastim should be administered approximately 24 hours after the completion of cytotoxic chemotherapy (for example, on Day 5 for patients in full-dose ifosfamide cohorts or Day 4 for patients in reduced-dose ifosfamide cohorts).
Sample collection									For all sample collection, see Appendix 4.
Pharmacodynamics									
Pharmacokinetics									
Immunogenicity									
Pharmacogenetics									
Other biomarkers									

Abbreviations: AE = adverse event; ASCO = American Society of Clinical Oncology; BSA = body surface area; C = cycle; CTCAE = Common Terminology Criteria for Adverse Events (NCI 2009); D = day; ECG = electrocardiogram; ECOG = Eastern Cooperative Oncology Group (Oken et al. 1982); G-CSF = granulocyte-colony stimulating factor; IRR = infusion-related reaction; IV = intravenously; LVEF = left ventricular ejection fraction; min = minutes; MUGA = multiple-gated acquisition; NCCN = National Comprehensive Cancer Network; PD = progressive disease; q = every; RBC = red blood cell; RECIST 1.1 = Response Criteria in Solid Tumors Version 1.1 (Eisenhauer et al. 2009).

^a Olaratumab monotherapy schedule applies to patients who have completed 6 cycles of olaratumab plus doxorubicin and ifosfamide and are continuing treatment with olaratumab monotherapy or have discontinued doxorubicin plus ifosfamide and are continuing with olaratumab monotherapy. Note: if a patient discontinues doxorubicin plus ifosfamide treatment prior to completing 6 cycles and is continuing treatment with olaratumab monotherapy, perform procedures according to the olaratumab monotherapy schedule beginning the next cycle after the patient discontinues doxorubicin/ifosfamide.

Table JGDR.3. Post-Treatment Follow-Up Schedule of Activities

Procedure	Short-Term Follow-Up ^a	Long-Term Follow-Up	Instructions
Visit	801	802-8XX	
Physical examination	X		Including weight and vital signs (temperature, blood pressure, pulse rate, respiration rate)
Concomitant medication	X		
AE collection	X		CTCAE Version 4.0.
ECOG performance status	X		
Radiologic imaging and measurement of palpable or visible lesions	X	X*	
*For patients whose disease has not progressed: Perform q 6 weeks × 2, then q 3 mo until:
 
 the patient has objective disease progression according to RECIST 1.1 or the study's primary/final analysis 
Perform using the same method used at baseline and throughout the study.
 
For patients who have had objective disease progression: Radiologic tests and measurement of palpable or visible lesions are no longer required; these patients should be followed up for OS and collection of post-study treatment anticancer therapy information collection as indicated below.

Collection of survival information		X	Perform q 2 mo (±7 days) for the first 2 years after discontinuation from study treatment and q 6 mo (±14 days) thereafter until death or study completion. If an in-person visit is not possible, confirm survival by contacting the patient directly via phone.
Collection of post-study treatment anticancer therapy information	X	X	Perform q 2 mo (±7 days) for the first 2 years after discontinuation from study treatment and q 6 mo (±14 days) thereafter until death or study completion.
ECG	X	X	
 All patients should have a 12-lead ECG performed at short-term follow-up. Patients should also have a 12-lead ECG performed approximately 6 months (±7 days) and 12 months (±7 days) after the end of treatment with doxorubicin and ifosfamide.

Procedure	Short-Term Follow-Up ^a	Long-Term Follow-Up	Instructions
Visit	801	802-8XX	
Echocardiogram and/or MUGA scan		X	Perform at 6 months (± 7 days) and 12 months (± 7 days) after the end of treatment with doxorubicin and ifosfamide. Echocardiograms/MUGA scans may be discontinued if the patient begins another anticancer therapy. Perform additional evaluations in the setting of cardiac symptoms and/or at the discretion of the investigator.
Hematology	X		See Appendix 3 . To be performed locally for patient management and centrally for analysis purposes.
Coagulation	X		See Appendix 3 . To be performed locally.
Clinical chemistry	X		See Appendix 3 . To be performed locally for patient management and centrally for analysis purposes.
Urinalysis	X		See Appendix 3 . To be performed locally.
Sample collection			For all sample collection, see Appendix 4 .
Pharmacodynamics			
Pharmacokinetics			
Immunogenicity			
Pharmacogenetics			
Other biomarkers			

Abbreviations: AE = adverse event; CTCAE = Common Terminology Criteria for Adverse Events (NCI 2009); ECOG = Eastern Cooperative Oncology Group (Oken et al. 1982); mo = month; MUGA = multiple-gated acquisition; OS = overall survival; q = every; RECIST 1.1 = Response Criteria in Solid Tumors Version 1.1 (Eisenhauer et al. 2009).

^a Short-term follow-up begins the day after the patient and the investigator agree that the patient will no longer continue study treatment and lasts approximately 30 days (± 7 days). No follow-up procedures will be performed for a patient who withdraws informed consent unless he or she has explicitly provided permission and consent.

Table JGDR.4. Continued Access Schedule of Activities

Visit	Study Treatment	Follow-Up ^a	Instructions
	501-5XX	901	
Procedure ^b			
AE collection	X	X	CTCAE Version 4.0 See Section 9.2.
Pharmacokinetics and immunogenicity		X	If a patient experiences an IRR, collect blood samples for pharmacokinetics and immunogenicity analysis at the following time points: (1) as soon as possible after the onset of the IRR, (2) at the resolution of the IRR and (3) 30 days after the IRR.
Administer olaratumab	X		21-day cycles Administer until PD, unacceptable toxicity, death, or other withdrawal criteria are met.

Abbreviations: AE = adverse event; CTCAE = Common Terminology Criteria for Adverse Events; IRR = infusion-related reaction.

- a Continued access follow-up begins 1 day after the patient and the investigator agree that the patient will no longer continue treatment in the continued access period and lasts approximately 30 days. No follow-up procedures will be performed for a patient who withdraws informed consent unless he or she has explicitly provided permission and consent.
- b Efficacy assessments will be done at the investigator's discretion based on the standard of care.

3. Introduction

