5.3. Study Completion Definition

The study will be considered complete 30 days after all patients in the Dose Confirmation Phase complete or discontinue olaratumab and doxorubicin, ifosfamide and mesna combination therapy. See Section 7.9 for details on treatment after the completion of the study.

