7.4.3.2.3. Monitoring for Doxorubicin-Associated Cardiotoxicity

Cardiotoxicity is a recognized risk of doxorubicin that increases with higher cumulative drug exposure. Cardiac monitoring is conducted by a combination of monitoring of clinical parameters, ECG, and echocardiogram (ECHO)/multiple-gated acquisition (MUGA) scan.

Changes in ECG, arrhythmias, tachycardia and/or chest pain should be managed based on the specific findings.

Patients will undergo baseline LVEF determination using ECHO or MUGA scan. This evaluation may be repeated at any time during the study if clinically indicated. A decrease in LVEF of \geq 10% and below the lower limit of normal, or an absolute decrease of 20%, or if the absolute LVEF decreases to or below 40%, then doxorubicin will be discontinued. Doxorubicin should also be discontinued if the patient develops Grade 3 or 4 left ventricular systolic dysfunction (symptomatic congestive heart failure).

The diagnostic method used at baseline for cardiovascular assessments (for example, ECHO or MUGA scans) should be the same method used throughout the study, unless there is clinical or instrumental evidence that further investigations are needed.

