5.8.8. Electrocardiograms, Echocardiogram / Multiple Gated Acquisition Scan

Electrocardiograms (ECG) findings that are considered to be a medical history condition or an AE will be summarized and listed.

Left ventricular ejection fraction (LVEF) results will be summarized by scheduled time point.

Changes in LVEF will also be summarized including percentage of patients with LVEF decrease of $\geq 10\%$ and below the lower limit of normal, or an absolute decrease of 20%, or an absolute LVEF decreases to or below 40%.

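### Some patients who stop chemotherapy early have no scheduled LVEF until about 6 months after doxorubicin, and the SAP's decline percentage counts those never rescanned as having no decline

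*Protocol*

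**What the plan says.** **Combination treatment.** In Protocol Table JGDR.2 the echocardiogram/MUGA instruction is "Perform at the end of C4 and C6; perform additional evaluations in the setting of cardiac symptoms and/or at the discretion of the investigator".

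**Early stop with olaratumab continued.** Footnote a of the same table tells sites to "perform procedures according to the olaratumab monotherapy schedule beginning the next cycle after the patient discontinues doxorubicin/ifosfamide". In that column the scan instruction is "For patients receiving olaratumab as monotherapy following discontinuation of combination therapy, perform approximately 6 months" (±14 days), and again at 12 months.

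**All study treatment stopped.** Protocol Table JGDR.3 leaves the echocardiogram/MUGA cell empty for short-term follow-up (Visit 801). Its instruction text names only 6 and 12 months (±7 days) after doxorubicin and ifosfamide end, and adds "Echocardiograms/MUGA scans may be discontinued if the patient begins another anticancer therapy".

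**ECG, by contrast.** Table JGDR.2 requires an ECG on Day 1 of Cycle 7. Table JGDR.3 says "All patients should have a 12-lead ECG performed at short-term follow-up".

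**Stated aim.** Protocol 3.2.1 explains that the amendment clarified the timing of ECHO/MUGA after chemotherapy and added ECGs with matching frequency, so that possible cardiotoxicity would be fully evaluated.

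**Analysis.** SAP 5.8.8 says "Left ventricular ejection fraction (LVEF) results will be summarized by scheduled time point". It then asks for the percentage of patients meeting LVEF-decline criteria. SAP 5.8 places safety analyses on the safety population, SAP 5.2.2 takes percentages relative to the population analysed, and SAP 5.3 imputes no missing data other than dates.

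**The concern.** The on-treatment scans hang on cycle numbers, not on the last doxorubicin dose. A patient who stops chemotherapy before reaching one of those cycle ends moves to a schedule whose next scan is about 6 months away.

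Safety is the primary objective, and cardiac dysfunction is an adverse event of special interest. If the patients without a timely scan are those who stopped for toxicity or progression, the LVEF results describe mainly the patients who tolerated four or six cycles. The SAP would then report a decline percentage without showing how many patients had no measurement behind it.

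**Working it through.** The plan states no figure on this point, so there is nothing to reproduce. The check is day arithmetic across the schedules.

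**Inputs**
- Cycle length 21 days (Protocol 7.2.1), taken without delays.
- Last doxorubicin dose on Day 3 of the cycle, 75 mg/m² planned per cycle (Protocol Table JGDR.6).
- One month = 365/12 days (SAP 5.2.2), so 6 months = 6 × 365/12 = 182.5 days.

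**Formulas**, for last doxorubicin in cycle k
- Day of last doxorubicin = 21(k − 1) + 3.
- Planned cumulative dose = 75k.
- Next scheduled scan = day 21k if k is 4 or 6 and the patient stays to the end of that cycle. Otherwise it is the last doxorubicin day + 182.5.

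| Last doxorubicin cycle | Day of last dose | Planned cumulative dose (mg/m²) | Last scheduled scan before it | Days to next scheduled scan |
|---|---|---|---|---|
| 1 | 3 | 75 | Baseline | 182.5 |
| 2 | 24 | 150 | Baseline | 182.5 |
| 3 | 45 | 225 | Baseline | 182.5 |
| 4, stays to cycle end | 66 | 300 | Baseline | 84 − 66 = 18 |
| 4, leaves all treatment earlier | 66 | 300 | Baseline | 182.5 |
| 5 | 87 | 375 | End of Cycle 4 (at 300) | 182.5 |
| 6, stays to cycle end | 108 | 450 | End of Cycle 4 | 126 − 108 = 18 |
| 6, leaves all treatment earlier | 108 | 450 | End of Cycle 4 (at 300) | 182.5 |

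The rows for Cycles 1, 2, 3 and 5 assume that ifosfamide stops too. The windows give 168.5 to 196.5 days on monotherapy (±14) and 175.5 to 189.5 days in follow-up (±7). For a Cycle 5 stopper the interval between scheduled scans is (87 + 182.5) − 84 = 185.5 days. Counting from a Day 4 ifosfamide dose instead adds one day.

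**Two exceptions**
- Footnote a changes the schedule only from the next cycle. A patient who stops chemotherapy during Cycle 4 but stays on olaratumab keeps the end-of-Cycle-4 scan.
- Protocol 7.4.2 allows either drug to be stopped separately, and the monotherapy column applies only when both are stopped. A patient who stops doxorubicin alone keeps any remaining Cycle 4 or 6 scan.

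**Schedule against stated aim.** At 6 and 12 months the ECG and ECHO/MUGA rows do coincide. They part at Cycle 7 Day 1 and at Visit 801, where ECG is required and LVEF is not. The 6- and 12-month windows also differ between Table JGDR.2 (±14 days) and Table JGDR.3 (±7 days).

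**Effect on the SAP percentage.** Let N be the safety population, m the number with no post-baseline LVEF, and e the number with an observed decline. Read literally, SAP 5.2.2 and 5.8 give e/N, while the rate among patients assessed is e/(N − m). The ratio of the two is (N − m)/N. With the planned 30 patients on the recommended regimen, one such patient gives 29/30 = 0.967. In a cohort of 15 it gives 14/15 = 0.933.

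**The case against.** The strongest reply is that this is a design choice. The protocol says "Cardiotoxicity is a recognized risk of doxorubicin that increases with higher cumulative drug exposure", and scans at planned doses of 300 and 450 mg/m² fit that statement; patients who stop in Cycles 1 to 3 have the lowest exposure. ECG and LVEF are different tests and need not share visits. Early stoppers still have ECGs, physical examination and adverse event collection through Visit 801, plus scans for symptoms or at discretion. The cardiac-dysfunction category in SAP Appendix 1 is built from preferred terms, not from scheduled LVEF alone. In SAP 5.8.8 the limit to scheduled time points governs the first summary only, so unscheduled and late scans can enter the decline percentage.

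Most of this stands, and it narrows what is at risk to asymptomatic decline in the months after chemotherapy. It does not explain why the stated aim of full cardiac evaluation is met with ECG alone at the two transition visits, and it does not settle the denominator.

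A reader might also infer stronger points that the documents do not support:
- *Early stoppers have no LVEF at all.* The 6- and 12-month scans are scheduled, and Cycle 5 stoppers also have the Cycle 4 scan. The waiver on new anticancer therapy is permissive and appears only in Table JGDR.3. The documents do not say how often such therapy starts.
- *Everyone who stops doxorubicin before the end of Cycle 4 or in Cycle 5 is affected.* The two exceptions above contradict this.
- *The numeric LVEF rule in Protocol 7.4.3.2.3 is defeated.* That rule governs stopping doxorubicin, and these patients have already stopped.
- *A count of affected patients can be given.* The documents contain no early-stopping rate.

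**Conclusion.** The concern holds for patients who stop both doxorubicin and ifosfamide with last dosing in Cycles 1 to 3 or 5, and for patients who leave all study treatment before the end of Cycle 4 or 6. Their first scheduled LVEF after doxorubicin comes at about 182 days, against about 18 days for those who complete Cycle 4 or 6. In follow-up that scan may be dropped once another anticancer therapy begins.

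Any patient left with no post-baseline LVEF is counted as a non-event. The decline percentage can then be too low but never too high, and it is understated whenever one of these patients had a decline. Patients whose only post-baseline scan came before their final doxorubicin dose add a separate weakness, because their value misses the last exposure.

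This rests on undelayed 21-day cycles, on planned doses (Protocol 7.4.3.2.1 provides for reductions, so actual cumulative doses may be lower), and on reading the SAP's percentage convention literally, since 5.8.8 names no other denominator. The number affected is unknown.

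**What to change.** 1. **Protocol.** Reconcile the echocardiogram/MUGA rows of Tables JGDR.2 and JGDR.3 with the ECG rows and with Protocol 3.2.1, including the ±14- and ±7-day windows. The schedule should state what LVEF assessment applies to patients who stop doxorubicin early. The monitoring rule itself is the sponsor's decision.

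2. **SAP 5.8.8.**
   - Base the decline percentage on patients with a baseline and at least one post-baseline LVEF, scheduled or unscheduled.
   - Add a summary of the last LVEF relative to the last doxorubicin dose, with cumulative dose.
   - Report the number of patients with no post-baseline LVEF, and the number with none after doxorubicin, by reason for stopping.

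The cost is table wording, a few SAP lines and slightly more analysis work. The stated denominator becomes smaller, but the patients without a measurement become visible.
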